## **Clinical Study Protocol** **Johnson & Johnson Vision Care, Inc.**

All adverse events occurring while the subject is enrolled in the study must be documented appropriately regardless of relationship.

It is the Investigator's responsibility to maintain documentation of each reported adverse event. All adverse events will be followed in accordance with applicable licensing requirements. Such documentation will include the following:

- Adverse event (diagnosis not symptom).
- Drawings or photographs (where appropriate) that detail the finding (e.g., size, location, and depth, etc.).
- Date the clinical site was notified.
- Date and time of onset.
- Date and time of resolution.
- Adverse event classification, severity, and relationship to test articles, as applicable.
- Treatment regimen instituted (where appropriate), including concomitant medications prescribed, in accordance with applicable licensing requirements.
- Any referral to another health care provider if needed.
- Outcome, ocular damage (if any).
- Likely etiology.
- Best corrected visual acuity at the discovery of the event and upon conclusion of the event, if the AE is related to the visual system.

Upon discovery of an AE that is deemed 'possibly related' or 'related' to the test article or study procedures (whether related to the visual system or not), an AE review form [REDACTED] must be completed. Additional dated and initialed entries should be made at follow-up evaluations. Separate forms must be completed for each eye if the AE is bilateral.

In addition, if an infiltrate(s) is present, he/she will complete the Corneal Infiltrate Assessment eCRF. Where necessary, a culture of the corneal lesion will be collected to determine if the infection is microbial in nature. If cultures are collected, the date of culture collection and laboratory utilized will be recorded.

Changes in the severity of an AE shall be documented to allow an assessment of the duration of the event at each level of intensity to be performed. Adverse events characterized as intermittent require documentation of the onset and duration of each episode. Changes in the assessment of relationship to the Test Article shall also be clearly documented.

Subjects who present with an adverse event shall be followed by the Investigator, within licensure, until all signs and symptoms have returned to pre-treatment status, stabilized, or been satisfactorily resolved. If further treatment beyond licensure is required, the patient will be referred to the appropriate health care provider. The Investigator will use his/her clinical judgment as to whether a subject reporting with an adverse event will continue in the study. If a subject is discontinued from the study, it will be the responsibility of the Investigator to record the reason for discontinuation. The Investigator will also document the adverse event appropriately and complete the Adverse Event eCRF. Any subjects with ongoing adverse events related to the test article, study treatment or study procedures, as of the final study visit

# **Clinical Study Protocol**

## **Johnson & Johnson Vision Care, Inc.**

date, should be followed to resolution of the adverse event or until referral to an appropriate health care provider, as recommended by the Investigator. Non-ocular adverse events that are not related to the test article, study treatment, or study procedures may be recorded as “ongoing” without further follow-up.

### **13.4. Reporting Adverse Events**

The Investigator will notify the Sponsor of an adverse event by e-mail, facsimile, or telephone as soon as possible and no later than 24 hours from discovery for any serious /significant adverse events, and 2 days from discovery for any non-significant adverse event. In addition, a written report will be submitted by the Principal Investigator to the IEC/IRB according to their requirements (section 13.4.2). The report will comment whether the adverse event was considered to be related to the test article, study treatment or study procedures.

#### **13.4.1. Reporting Adverse Events to Sponsor**

##### **Serious/Significant Adverse Events**

The Investigator will inform the sponsor of all serious/significant adverse events occurring during the study period as soon as possible by e-mail or telephone, but no later than 24 hours following discovery of the event. The Investigator is obligated to pursue and obtain information requested by the Sponsor in addition to that information reported on the eCRF. All subjects experiencing a serious/significant adverse event must be followed up and all outcomes must be reported.

When medically necessary, the Investigator may break the randomization code to determine the identity of the treatment that the subject received. The Sponsor and study monitor should be notified prior to unmasking the test articles.

In the event of a serious/significant adverse event, the Investigator must:

- Notify the Sponsor immediately.
- Obtain and maintain in the subject’s records all pertinent medical information and medical judgment for colleagues who assisted in the treatment and follow-up of the subject.
- Provide the Sponsor with a complete case history which includes a statement as to whether the event was or was not related to the use of the test article.
- Notify the IEC/IRB as required by the IEC/IRB reporting procedure according to national regulations.

##### **Unanticipated (Serious) Adverse Device Effect (UADE)**

In the event of an Unanticipated (Serious) Adverse Device Effect (UADE), the Investigator will submit a report of the UADE to the Sponsor and IEC/IRB as soon as possible, but no later than 24 hours after the Investigator first learns of the effect. This report is in addition to the immediate notification mentioned above.

The Sponsor must conduct an evaluation of the UADE and must report the results of the evaluation to FDA, the IEC/IRB and participating Investigators within 10 working days after the Sponsor first receives notification of the effect.

# **Clinical Study Protocol**

## **Johnson & Johnson Vision Care, Inc.**

### **Non-Serious Adverse Events**

All non-serious adverse events, including non-serious adverse device effects, will be reported to the sponsor by the Investigator no later than 2 days from discovery.

#### **13.4.2. Reporting Adverse Events to the Responsible IEC/IRB and Health Authorities**

Adverse events that meet the IEC/IRB requirements for reporting must be reported within the IEC/IRB's written guidelines. Each clinical site will refer to and follow any guidelines set forth by their Approving IEC/IRB. Each clinical site will refer to and follow any guidelines set forth by their local governing Health Authorities.

The Sponsor will report applicable Adverse Events to the local health authorities according the written guidelines, including reporting timelines.

#### **13.5. Event of Special Interest**

None.

#### **13.6. Reporting of Pregnancy**

Subjects reporting pregnancy (by self-report) during the study will be discontinued after the event is recorded as an Adverse Event. Once discontinued, pregnant participants and their fetuses will not be monitored for study related purposes. Pregnant participants are not discontinued from contact lens or solution related studies for safety concerns, but due to general concerns relating to pregnancy and contact lens use. Specifically, pregnant women are discontinued due to fluctuations in refractive error and/or visual acuity that occur secondary to systemic hormonal changes, and not due to unforeseen health risks to the mother or fetus.

## **14. STATISTICAL METHODS**

#### **14.1. General Considerations**

Statistical Analysis will be undertaken by the sponsor or under the authority of the sponsor. A general description of the statistical methods to be implemented in this clinical trial is outlined below.

All data summaries and statistical analyses will be performed using the SAS software Version 9.4 or higher (SAS Institute, Cary, NC). Throughout the analysis of data, the results for each subject/eye will be used when available for summarization and statistical analysis. Unscheduled visits will be summarized separately and will be excluded from the statistical analysis.

Summary tables (descriptive statistics and/or frequency tables) will be provided for all baseline variables, efficacy variables and safety variables as appropriate. Continuous variables will be summarized with descriptive statistics (n, mean, standard deviation (SD), median, minimum and maximum). Frequency count and percentage of subjects or eyes within each category will be provided for categorical data.

# Clinical Study Protocol

## Johnson & Johnson Vision Care, Inc.

### 14.2. Sample Size Justification

For phase 1, the plan is to enroll approximately 24 eligible subjects with 20 subjects targeted to complete this phase. The sample size was not based on any empirical sample size calculation. The sample size was chosen based on resources in conjunction, subject matter experts, and any available literature. To help ensure the glare source intensity, a small pilot investigation per the ANSI Z80.12-2007 standard was interpreted to be about 20 subjects to complete phase 1, which should be sufficient to evaluate the mean photopic and mesopic contrast sensitivity with and without the glare source.

For phase 2, the plan is to enroll approximately 66 eligible subjects with 60 subjects targeted to compete the study. Given no historical data is available for the primary and secondary endpoints with the study lenses under the specific light source condition, the sample size was not determined based on any empirical sample size calculation. A power analysis for the primary and secondary endpoints was conducted to estimate statistical power based on historical data for similar endpoints (i.e., CSF and logMAR visual acuity using different instruments) with different assumptions and sample sizes.

Historical monocular logMAR visual acuity (VA) data from [REDACTED] and binocular AULCSF data for qCSF testing from [REDACTED] were summarized in *Table 8* below. The assessments were conducted under conditions without a broadband light source in both studies. [REDACTED] was a 5×5 crossover design and two of the five study lenses were senofilcon A with new UV/HEV blocker and 1-Day ACUVUE OASYS. Data for these two lenses were used as a basis to make assumptions for the Test and Control lenses in the current study. [REDACTED] was a 2×3 crossover design with ACUVUE OASYS and senofilcon A with new UV-blocker lenses. The AULCSF using the qCSF method in the first two periods from [REDACTED] were summarized and used as a bases for making assumptions for testing the AULCSF with the Metropsis system between the Test and Control lenses in the current study.

Table 8: Descriptive Summary of LogMAR Visual Acuity and AULCSF from qCSF testing based on Historical Data – Completed Per Protocol Subjects

Study ID	Endpoint	Condition	Lens	Mean	Standard Deviation
[REDACTED]	LogMAR VA at Fitting	Low Luminance High Contrast	Theia	0.020	0.092
			Acuvue Oasys 1-Day	0.022	0.079
[REDACTED]	AULCSF for qCSF at 2-week Follow-up	NA	Senofilcon A with new UV-blocker	1.31	0.110
			Acuvue Oasys	1.29	0.111

Considering different number of subjects to complete the study (i.e., 50, 60, and 70), a power analysis was conducted for the primary and secondary hypotheses based on the assumptions for correlation between measures from left and right eyes within subjects, standard deviation,

**Clinical Study Protocol**  
**Johnson & Johnson Vision Care, Inc.**

and effect size (i.e., mean difference). Power was estimated using a paired sample *t*-test (exact method) with a 2-sided type I error rate of alpha = 0.05 for the primary endpoint and a Bonferroni adjusted 2-sided type I error rate (alpha = 0.025) for each secondary endpoint. The calculation was performed using the POWER procedure in SAS Version 9.4. *Table 9* below shows the estimated statistical power under different scenarios. Given time and resource constraints, sixty subjects have been considered as the optimal number which demonstrated an acceptable level of statistical power under most assessed scenarios. Therefore, the plan is to enroll approximately 66 eligible subjects with 60 subjects targeted to complete the study.

Table 9: Power Analysis for the Primary and Secondary Hypotheses (Superiority Testing)

Endpoints	Mean Difference (Test - Control)	Standard Deviation (Test)	Standard Deviation (Control)	Correlation	Completed Subjects	Power
Primary Endpoint: Photopic Resolution Acuity with a Glare Source (converted to logMAR)	-0.05	0.08	0.09	0.3	50	93.0%
					60	96.5%
					70	98.3%
				0.5	50	98.2%
					60	99.4%
					70	99.8%
		0.10	0.11	0.3	50	79.5%
					60	86.4%
					70	91.2%
				0.5	50	90.8%
					60	95.1%
					70	97.5%
Secondary Endpoint: AULCSF for Mesopic Contrast Sensitivity with a Glare Source	0.06	0.13	0.13	0.3	50	67.2%
					60	76.3%
					70	83.2%
				0.5	50	82.6%
					60	89.6%
					70	93.9%
		0.15	0.15	0.3	50	53.5%
					60	62.6%
					70	70.4%
				0.5	50	69.6%
					60	78.5%
					70	85.2%
Secondary Endpoint: AULCSF for Photopic Contrast Sensitivity	0.06	0.11	0.11	0.3	50	82.5%
					60	89.5%
					70	93.9%
				0.5	50	93.5%
					60	97.1%
					70	98.7%

**Clinical Study Protocol**  
**Johnson & Johnson Vision Care, Inc.**

Endpoints	Mean Difference (Test - Control)	Standard Deviation (Test)	Standard Deviation (Control)	Correlation	Completed Subjects	Power
with a Glare Source		0.13	0.13	0.3	50	67.2%
					60	76.3%
					70	83.2%
				0.5	50	82.6%
					60	89.6%
					70	93.9%

#### **14.3. Analysis Populations**

The following analysis populations will be defined and used in the analysis and presentation of the data.

##### **All Enrolled:**

All Enrolled Population includes all subjects with recorded data in the electronic Case Report Form (eCRF) database.

##### **Safety Population:**

All subjects who are administered any test article excluding subjects who drop out prior to administering any test article. At least one observation should be recorded. Subjects will be analyzed as per treatment received.

##### **Per-Protocol Population:**

All subjects who successfully complete all visits and do not substantially deviate from the protocol as determined by the trial cohort review committee prior to database hard lock. Justification for the exclusion of subjects with protocol deviations from the per-protocol population set will be documented in a memo to file.

##### **Intent-to-Treat (ITT) Population:**

All randomized subjects regardless of actual treatment and subsequent withdrawal from the study or deviation from the protocol. At least one observation should be recorded. Subjects will be analyzed as per randomized treatment.

#### **14.4. Level of Statistical Significance**

All planned analysis for this study will be conducted with an overall type I error of 5% using a gatekeeping testing strategy and Bonferroni adjustment. The primary analysis will be conducted with a two-sided type I error rate of 0.05. Alpha will be shared between the two secondary endpoints using Bonferroni method; each secondary hypothesis will be tested at the two-sided type I error of 0.025 (0.05/2). The secondary hypotheses will be assessed only when the primary hypothesis is met.

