#### Hypothesis Testing

The null and alternative hypotheses for testing superiority of the Test Lens compared to the Control lens with respect to AULCSF for photopic contrast sensitivity with a broadband light source are presented below:

$$H_0: \mu_T - \mu_C \leq 0$$
$$H_A: \mu_T - \mu_C > 0$$

Where,  $\mu_T$  represents the mean AULCSF for the Test lens and  $\mu_C$  represents the mean AULCSF for the Control lens. Statistical superiority will be declared if the lower bound of the 2-sided 95% confidence interval of the mean difference (Test – Control) is larger than 0. A model-based point estimate of the mean difference being 0.06 log or more ( $\geq 0.06$  log) will be considered clinically meaningful.

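### The fixed Bonferroni split for the two secondaries is valid but gives up power that Holm keeps at the same 5% error, and the 95% interval rule in 14.6 contradicts it

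*Combined protocol and SAP*

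**What the plan says.** Section 14.4 promises an "overall type I error of 5% using a gatekeeping testing strategy and Bonferroni adjustment". The primary is tested at two-sided 0.05. The gate is explicit: "The secondary hypotheses will be assessed only when the primary hypothesis is met". Behind it, "Alpha will be shared between the two secondary endpoints using Bonferroni method", at two-sided 0.025 each. Nothing lets one secondary use the other's share once that other has succeeded.

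Section 14.2 powers the secondaries on the same basis, with a "Bonferroni adjusted 2-sided type I error rate (alpha = 0.025) for each secondary endpoint". The sample size is to "enroll approximately 66 eligible subjects with 60 subjects targeted to complete the study". At 60 completers Table 9 gives 62.6% to 89.6% for mesopic and 76.3% to 97.1% for photopic contrast sensitivity.

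The decision rule in section 14.6 is different. For photopic contrast sensitivity, "Statistical superiority will be declared if the lower bound of the 2-sided 95% confidence interval of the mean difference" exceeds zero, and mesopic is to be handled in the same way. The 0.025 level does not appear in that rule. Sections 2.3 and 14.6 also compare each point estimate with a clinical margin of 0.06 log.

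**The concern.** There are two issues in the same few sentences.

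The first is efficiency. Under plain Bonferroni the second endpoint stays at 0.025 even when the first has been rejected. Holm would release it to 0.05 without raising the familywise error. Mesopic contrast sensitivity is the weakest endpoint in Table 9, and section 14.2 says 60 was settled on under time and resource constraints, so power that needs no further subjects has some value.

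The second is consistency. Sections 14.4 and 14.6 set different levels for the same tests. A secondary result with a two-sided p-value between 0.025 and 0.05 would fail under one section and pass under the other, so the analyst would have to choose after seeing the data.

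**Working it through.** **Inputs.** From section 14.2 and Table 9: true difference 0.06; n = 60; between-eye correlation r = 0.3 or 0.5; SD 0.15 or 0.13 (mesopic) and 0.13 or 0.11 (photopic); paired t-test at two-sided 0.025. Matched scenarios pair the higher SDs (0.15/0.13) or the lower SDs (0.13/0.11). The correlation ρ between the two endpoints' Test − Control differences is not in the documents. It is assumed to be 0, 0.3, 0.5 or 0.8.

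**Step 1: reproduce Table 9.** SD of the difference = √(s₁² + s₂² − 2·r·s₁·s₂). For mesopic, SD 0.15, r = 0.3: √(0.0225 + 0.0225 − 0.0135) = √0.0315 = 0.1775. Standard error = 0.1775/√60 = 0.0229. Noncentrality = 0.06/0.0229 = 2.62 on 59 df. Exact power at 0.025 is 62.6%, as printed. All 24 secondary entries and all 12 primary entries reproduce to 0.1 point.

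**Step 2: the most that could be recovered.** This is power at 0.05 less power at 0.025, n = 60.

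| Endpoint, SD | r | 0.025 | 0.05 | Gap |
|---|---|---|---|---|
| Mesopic 0.15 | 0.3 | 62.6% | 73.1% | 10.5 |
| Mesopic 0.15 | 0.5 | 78.5% | 86.2% | 7.6 |
| Mesopic or photopic 0.13 | 0.3 | 76.3% | 84.4% | 8.1 |
| Mesopic or photopic 0.13 | 0.5 | 89.6% | 94.0% | 4.5 |
| Photopic 0.11 | 0.3 | 89.5% | 94.0% | 4.5 |
| Photopic 0.11 | 0.5 | 97.1% | 98.6% | 1.5 |

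**Step 3: error control under Holm.** Reject an endpoint if p ≤ 0.025, or if p ≤ 0.05 and the other endpoint has p ≤ 0.025. If both nulls are true, any rejection needs at least one p ≤ 0.025, so the error is at most 0.025 + 0.025 = 0.05 under any dependence. If one null is true, it is never tested above 0.05. Simulation agrees: 4.9%, 4.7% and 4.0% with both nulls true (ρ = 0, 0.5, 0.8), and 5.0% with one true.

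**Step 4: power under Holm.** Simulated correlated paired t statistics, 400,000 draws per scenario, n = 60. Ranges run over ρ = 0 to 0.8.

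| SD mesopic/photopic | r | Mesopic | Gain | Photopic | Gain | Gain, both succeed |
|---|---|---|---|---|---|---|
| 0.15/0.13 | 0.3 | 62.6% → 70.2–70.6% | 7.5–8.0 | 76.3% → 78.7–81.4% | 2.3–5.1 | 9.9–13.1 |
| 0.15/0.13 | 0.5 | 78.5% → 84.7–85.4% | 6.1–6.8 | 89.6% → 91.0–93.1% | 1.4–3.5 | 7.4–10.3 |
| 0.13/0.11 | 0.3 | 76.3% → 83.1–83.6% | 6.8–7.2 | 89.5% → 90.7–92.9% | 1.2–3.4 | 7.9–10.7 |
| 0.13/0.11 | 0.5 | 89.6% → 93.6–93.9% | 4.0–4.4 | 97.1% → 97.5–98.4% | 0.4–1.4 | 4.4–5.7 |

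Allowing every SD pairing widens the gains to 2.6–9.6 (mesopic) and 0.1–6.2 (photopic). The chance that at least one succeeds does not move, because Holm cannot start without a p ≤ 0.025.

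**Step 5: where the extra successes fall.** With SD 0.15 and r = 0.3, significance needs an estimate of about 2.300 × 0.0229 = 0.053 at 0.025, and 2.001 × 0.0229 = 0.046 at 0.05. At the planned SD, an estimate of 0.06 therefore already passes Bonferroni. In simulation about 97.5% of Holm's extra mesopic successes in that scenario, and essentially all extra photopic ones, lie below 0.06. The chance of mesopic being both significant and at least 0.06 goes from 49.7% to 49.9% there and does not change in the other three scenarios.

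**Step 6: section 14.6 read literally.** A lower 95% limit above zero is a test at two-sided 0.05. On the plan's two-sided count, two such tests spend 1 − 0.95² = 9.75% if independent and at most 0.05 + 0.05 = 10%. Counting only false claims in favour of the Test lens halves this: at most 0.025 + 0.025 = 5%, against 0.0125 + 0.0125 = 2.5% under 14.4.

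**The case against.** Fixed 0.025 per secondary is valid, prespecified and consistent with Table 9. The sponsor showed the resulting power and accepted it. Section 2.3 rests the study objective on the primary alone. All of that stands: choosing Holm is a gain in efficiency, not the repair of an invalid test.

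The clinical-margin argument also stands. The gain is in declarations of statistical superiority, and almost none of the added declarations would meet the plan's 0.06 criterion. It does not remove the point, because 14.6 declares superiority on the interval alone and the margin is a separate reading.

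Three stronger readings are tempting and should be resisted:

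- A reader might infer that each secondary loses several points of power. Photopic often gains under 3 points, and as little as 0.4 in the matched scenarios.
- A reader might infer that Holm is worth ten completers, since Table 9 needs 70 to reach 70.4% for mesopic. That equivalence belongs to the least favourable scenario (SD 0.15, r = 0.3).
- A reader might infer that the plan has set its secondary error at 10%. The documents do not support that. Sections 14.2 and 14.4 both state 0.025, and only the 14.6 rule departs from it.

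It could be said that 14.6 means a Bonferroni-adjusted interval. The text does not say so, and the word adjusted is attached to the primary's interval in 14.5, not to this one.

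**Conclusion.** Both parts hold. Holm behind the existing gate dominates the fixed split at the same 5% familywise error. At n = 60 it is worth about 4 to 8 points for mesopic, 0.4 to 5 for photopic, and 4 to 13 for both succeeding. It adds nothing to the chance of at least one success and almost nothing to results that reach the 0.06 margin.

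The figures rest on Table 9's SDs, eye correlations and paired t-test, and on an assumed endpoint correlation of 0 to 0.8. The mesopic gain hardly depends on that correlation; the photopic gain does. All are conditional on passing the primary gate, for which Table 9 gives 86.4% to 99.4% at n = 60. If passing were independent of the secondaries, an 8.0-point gain would shrink to at worst 8.0 × 0.864 = 6.9.

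The conflict between 14.4 and 14.6 needs no assumption. It must be resolved whichever procedure is chosen.

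**What to change.** - **Section 14.4:** after the primary gate, replace Bonferroni with Holm. Test the smaller p-value at two-sided 0.025. Test the other at two-sided 0.05 only if the first is rejected in favour of the Test lens.
- **Section 14.6:** replace the 95% rule with the matching one. Judge both endpoints by 97.5% intervals; if one succeeds, judge the other by its 95% interval. State that this is a decision rule and not a pair of simultaneous 95% intervals, since a 97.5% and a 95% interval together guarantee only 1 − (0.025 + 0.05) = 92.5%.
- **Table 9:** re-run the secondary rows under Holm over a stated range of endpoint correlation, and say that they are conditional on the gate.
- **If Bonferroni is kept:** change 14.6 to 97.5% intervals for both secondaries.

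The cost is a few sentences and one re-run of the power table, fixed before unmasking. No subjects, visits or procedures are added.
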